#### *Sample size calculation*

- a. For the long-term effectiveness evaluation, the difference in 5-year incidence of CVD between the RAMP-HT and usual care group is the primary outcome. From the result of our RAMP-HT QOC study, the observed 1-year incidence of CVD in the RAMP-HT and usual care group was 1.33% and 1.76% respectively. A conservative estimate of the 5-year incidence of CVD in RAMP-HT and usual care group would be 7% and 8%, respectively. A minimum sample size of 7,116 subjects from each group will be needed to detect a difference of 1% in incidence rates of CVD between RAMP-HT and usual care group with 90% power and at 5% level of significance.

We have identified from the HA CMS data set of the RAMP-HT QOC study 8,681 eligible RAMP-HT patients and 8,681 usual care patients who fulfilled the inclusion criteria and without any exclusion criterion matched by propensity score matching. These two matched cohorts will be the subjects of this long-term effectiveness and cost-effectiveness

study. The flow chart of subject selection is attached in Appendix C.

- b. For the costing analysis, 140 subjects from each of the RAMP-HT and usual care groups will be required to show that the direct medical costs of RAMP-HT patients (excluding RAMP cost) is not higher than that of usual care HT patients by independent one side t-test with 0.3 effect size and 80% power at 5% significance level.

307 RAMP-HT and 291 usual care patients had been recruited from May 2013 to March 2014 in GOPCs across Hong Kong for the longitudinal evaluation of patient reported outcomes (PRO) in the RAMP-HT QOC study. These patients will be follow-up from May 2015 to March 2016 as part of our RAMP-HT QOC study; telephone survey on private health service utilization will be conducted at the same time. Taking 25% attrition rate into account, 230 RAMP-HT and 218 usual care patients will complete the questionnaire. This sample will be adequate for the comparison of private medical cost between RAMP-HT and usual care group.

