**Long Term Effectiveness of RAMP-HT**

Descriptive statistics will be performed on the clinical parameters (e.g. blood pressure (BP), lipid profile, BMI) and incidence of CHD, heart failure, stroke, ESRD, HT-related mortality and all-cause mortalities of the RAMP-HT and usual care cohorts. Differences in each outcome between groups will be tested using independent t-tests for continuous variables such as mean BP, or chi-square tests for categorical variables such as proportion of patients with BP control or CVD incidence. The number needed to treat to reduce one CVD, each specific HT complication and death by RAMP-HT will be calculated from the unadjusted 5-year rates between RAMP-HT and usual care HT cohorts.

Multivariable Cox proportional hazards regression will be performed to estimate the adjusted effect of RAMP-HT on the dependent variable of each first HT complication event, adjusting for all baseline covariates of patients. Cox model has been widely used to evaluate the effectiveness of primary care intervention in previous study. For each model, survival curves will be estimated by Kaplan-Meier method and the differences between RAMP-HT and usual care groups will be compared using the

log-rank test. The effectiveness of RAMP-HT will be measured by Hazard ratio with 95% confidence intervals in the regression models. Predictive accuracy of Cox models will be assessed and compared using Harrell's discrimination C-index, ranging from zero to one. A value of 0.5 indicates no predictive discrimination, and values of 0 or 1.0 indicate perfect separation of patients. Goodness-of-fit for Cox regression model will be assessed using Akaike information criterion and Bayesian information criterion.

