### **Health Preference by HT Complication Status**

The SF-6D preference will be calculated by the HK population specific

algorithm^15 by HT complication status. Independent t-test will be used to compare the SF-6D values of HT patients with each complication to those without any complication, and between RAMP-HT and usual care HT patients.

All above statistical analyses will be performed using STATA Version 13.0 (StataCorp LP. College Station, Texas, U.S.). All significance tests will be two-tailed and those with a p-value less than 0.05 will be considered statistically significant.

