3. HT patients with complications may die from either HT-related death or other cause of death.
4. RAMP-HT is effective in reducing HT complications for a period of 5 year; thus the transition probability adjustment of CVD/ESRD development (as determined by the annualized hazard ratio obtained from our long-term effectiveness analysis) will be applied to the model of the RAMP-HT cohort in the first five years. After 5 years, the RAMP-HT will have the same transition probabilities of developing HT complications as usual care HT cohort.
5. RAMP-HT is repeated every 12-24 months and the effectiveness of RAMP-HT will not decrease over time; thus the 5-year effect of RAMP-HT can be annualized. Adjustment will be made on the average duration of repeat RAMP-HT based on available empirical data in order to avoid over-estimation of the RAMP-HT cost.
6. The medical cost (public and private) of HT patients in usual care and RAMP-HT programme is the same for the same HT health status except for the additional RAMP-HT cost.
7. All costs and health preference will be discounted by an annual rate of 3.5% as recommended by the guidance of National Institute for Health and Clinical Excellence (National Institute for Clinical Excellence 2008).

[Word Count: 3968 ]

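### No proportional-hazards check is planned for the Cox model, yet its hazard ratio enters the Markov model as a constant, undefined annualized effect

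*Combined protocol and SAP*

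**What the plan says.** In Long Term Effectiveness of RAMP-HT (section d(v)), the effect on each first complication is a covariate-adjusted Cox hazard ratio. On model fit, the plan says: "Goodness-of-fit for Cox regression model will be assessed using Akaike information criterion and Bayesian information criterion". Harrell's C-index, Kaplan-Meier curves and log-rank tests are also planned. The section specifies no residual-based diagnostic, group-by-time term or period-specific hazard ratio.

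In the Markov assumptions, item 4 adjusts the RAMP-HT transition probabilities for the first five years, "as determined by the annualized hazard ratio obtained from our long-term effectiveness analysis". After that, both arms share the same probabilities. Item 5 takes the programme's effectiveness as undiminished over time, "thus the 5-year effect of RAMP-HT can be annualized". The footnote to Table 1 applies the hazard ratio to coronary heart disease, stroke, heart failure and end-stage renal disease.

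The opening text of the Markov section describes something else: yearly transition probabilities estimated from the complication rates observed in each cohort.

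The only rates given are in Sample size calculation, item a: "the observed 1-year incidence of CVD in the RAMP-HT and usual care group was 1.33% and 1.76% respectively", and "A conservative estimate of the 5-year incidence of CVD in RAMP-HT and usual care group would be 7% and 8%, respectively".

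**The concern.** There are two gaps, and they compound each other.

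First, AIC and BIC compare candidate models. They can speak to proportional hazards only if a model with a time-varying effect is among the candidates, and none is planned. The C-index measures discrimination. Kaplan-Meier curves could reveal a gross departure, but they are planned for a log-rank comparison and not as a diagnostic.

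Second, the model takes a constant effect as given and passes it on through an undefined operation. A five-year risk has to be converted to an annual one. A hazard ratio does not, because it already compares rates. An analyst who follows the wording literally could shrink the effect considerably, and the two descriptions of the transition probabilities do not settle which calculation is meant.

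The ICER is a primary outcome, and hypothesis 4 compares it with a threshold. The Markov section names no sensitivity analysis that would expose a wrong choice.

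**Working it through.** **The plan's own figure.** The documents state no hazard ratio. The one figure built on the five-year rates is the sample size: "A minimum sample size of 7,116 subjects from each group will be needed to detect a difference of 1% in incidence rates of CVD", "with 90% power and at 5% level of significance", with "All significance tests will be two-tailed and those with a p-value less than 0.05 will be considered statistically significant". The unpooled formula gives (1.960 + 1.282)² × (0.07×0.93 + 0.08×0.92) / 0.01² ≈ 14,574 per group (14,577 with pooled variance), so 7,116 does not reproduce. It is about half the required number. That is a separate matter, and nothing below uses 7,116.

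**Inputs.** Observed one-year CVD incidence is 1.33% (RAMP-HT) and 1.76% (usual care). Planning five-year incidence is 7% and 8%. Cumulative hazard is H = −ln(1 − risk).

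**1. Hazard ratios implied by these rates**
- Year 1: 0.01339 / 0.01776 = 0.754
- Five years: 0.07257 / 0.08338 = 0.870
- Years 2 to 5: (0.07257 − 0.01339) / (0.08338 − 0.01776) = 0.902
- Holding 0.754 for five years against 8%: 1 − 0.92^0.754 = 6.1%, not 7%

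The planning rates therefore do not fit a constant effect at the observed year-1 level.

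**2. What annualizing does**
- Direct use: with a constant hazard, the usual-care annual probability is 1 − 0.92^(1/5) = 1.65%. Using p_RAMP = 1 − (1 − p_UC)^0.870 in each of five cycles gives 1 − 0.92^0.870 = 7.0%, a reduction of 1.0 point.
- Fifth root: 0.870^(1/5) = 0.973. Then 1 − 0.92^0.973 = 7.79%, a reduction of 0.21 points. This removes 79% of the modelled reduction.

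**3. How firm the 0.902 is**
- If each five-year rate may be off by 0.5 points, the years 2 to 5 value runs from 0.76 (6.5% v 8.5%) to 1.07 (7.5% v 7.5%).
- Extending the year-1 hazards unchanged gives 6.5% and 8.5% at five years.
- Assume that the one-year rates apply to 8,681 per group, which the documents do not say. Year-1 events are then about 115 and 153, the standard error of the log hazard ratio is √(1/115.5 + 1/152.8) = 0.123, and the 95% interval for 0.754 is 0.59 to 0.96. That interval includes 0.87 and 0.90.

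**4. Power to detect a change from 0.75 to 0.90**
- On the same assumption, later events are about 492 and 542, with standard error 0.062.
- z = (ln 0.902 − ln 0.754) / √(0.123² + 0.062²) ≈ 1.30, so power is Φ(1.30 − 1.96), about 25%.

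**5. Constant against period-specific hazard ratios, applied directly**
- Both give 10.0 fewer events per 1,000 at year 5.
- Event-free years gained per 1,000 over five years (year-end counts) are 31.0 with a constant 0.870 and 36.0 with 0.754 followed by 0.902.

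**The case against.** The strongest reply is that the wording is loose but the intention harmless. No fifth root appears anywhere. Table 1 simply says the hazard ratio will be applied to the transition probabilities, and annualizing may mean no more than using the effect in yearly cycles. That reading is plausible, and the 0.21-point figure must not be presented as the plan's method. What stands is that the term is undefined and the readings differ almost fivefold.

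A second reply also stands. On these rates a correctly applied constant hazard ratio leaves five-year events unchanged and slightly understates the event-free time gained.

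A reader might go further in four ways that the documents do not support:
- **That the effect wanes.** The 0.902 combines an observed rate with a rounded planning rate that the plan labels conservative. It may reflect only that conservatism.
- **That most of the benefit falls in year 1.** The planned risk difference is 0.43 points at one year and 1.00 at five, so 57% arises later.
- **That the known year-1 result inflates the error rate of the five-year test by a calculable amount.** The denominator behind the one-year rates is not given, and any such figure treats the year-1 difference as pure chance.
- **That years 2 to 5 would be an untouched confirmation.** Data Collection has three-year data available by November 2015, and the Timeline schedules a three-year interim analysis and a preliminary ICER before the five-year extraction.

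**Conclusion.** The concern holds as a gap in specification. The plan has no check of proportional hazards, AIC and BIC cannot serve as one here, and the step from Cox model to Markov model is undefined and described in two ways.

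The size depends on how the step is read. On 7% v 8% with a constant hazard, the modelled five-year reduction is 1.0 point if the hazard ratio is used directly and about 0.21 points if its fifth root is used. Non-proportionality alone, at the illustrative 0.754 and 0.902, matters much less: 31.0 against 36.0 event-free years per 1,000. These values show only that the planning assumptions do not match a steady effect at the year-1 level. The size cannot be carried through to QALYs, because the documents give no utility or cost values for the model.

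**What to change.** 1. In Long Term Effectiveness of RAMP-HT, specify Schoenfeld residuals and a group-by-time term as the check of proportional hazards, in place of AIC and BIC or in addition to them.
2. Report period-specific hazard ratios, for example year 1 and years 2 to 5, whatever the test shows, because its power may be only about 25%. Run the Markov model with them as a sensitivity analysis.
3. In Markov assumptions 4 and 5, delete the word annualized. State p_RAMP = 1 − (1 − p_UC)^HR for each annual cycle, using the Cox hazard ratio for the endpoint concerned.
4. Reconcile the opening description of transition probabilities with assumptions 4 and 5, and say which route is the base case.

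This needs no new data, only some wording and a few extra model runs. The price is that period-specific hazard ratios have wider intervals than the pooled one. The later-period value also compares only patients still event-free, so it should be read as descriptive.

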### **Cost Analysis of RAMP-HT**

Descriptive statistics will be used to summarize the costs of RAMP-HT and annual direct medical costs for RAMP-HT and usual care patients at baseline and over each of 5 subsequent years, overall, and by the presence of complications. The cost of each healthcare service will be derived by multiplication of the unit cost from Gazette and Hospital Authority ordinance and the number of respective services used by the patients. To avoid double counting the cost of drugs and laboratory tests, the Government Gazette cost of each GOPC and SOPC attendance will be adjusted by a factor of 0.7 to include only the manpower cost. The total public medical costs will be calculated by summing up all costs of drugs, laboratory tests and each healthcare service utilisation. The private medical costs will be estimated by summarizing the self-reported costs of private consultations, self-medication and private hospitalisation. The average annual public and private direct medical costs per patient will be analysed by HT complication status (CHD, heart failure, stroke and ESRD), and by RAMP-HT and usual care HT groups. To determine whether the direct medical costs of the RAMP-HT cohort is higher than the usual care HT cohort, one sided independent t-test will be performed.

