#### *(ii) Direct Medical Costs of HT patients*

The medical cost analysis will focus on the direct medical costs involved in the care of HT patients without or with specific HT complications (i.e. CHD, heart failure, stroke and ESRD) in both public and private healthcare sectors; indirect cost (e.g. opportunity cost) and non-medical costs (e.g. transportation cost, carer cost) will not be measured.

Public medical costs will be estimated from products of the unit costs (published in the HKSAR Government Gazette and Hospital Authority ordinance (Chapter 113) of charges for non-entitled persons) and the utilization rates of 1) dispensed drugs (*note: self-financed drugs will be considered as private medical cost, see below*), 2) laboratory tests and investigations, 3) healthcare services including general outpatient clinics (GOPC), specialist outpatient clinics (SOPC), allied health services (e.g. dietician, physiotherapist or occupational therapist), accident and emergency (A&E) department and 4) admissions to hospital in the 12 months before baseline and at 12, 24, 36, 48 and 60 months after study enrolment for each patient in the study cohorts. The data extraction will be carried out by the HA statistics team.

Private direct medical costs include the cost of all private Western doctor and Chinese medicine practitioner consultations, private hospitalisation and self-medications inclusive of self-financed medications prescribed by the HA. 598 HT patients (307 RAMP-HT patients and 291 usual care patients) who were recruited from HA GOPCs for the longitudinal evaluation of patient reported outcomes (PRO) in the evaluation of QOC RAMP-HT study from May 2013 to March 2014 will be invited to complete a “private medical cost of HT questionnaire” (Appendix E) by telephone. The questionnaire is adapted from the costing questionnaire that was used in our in-depth study on the cost-effectiveness analysis of RAMP-DM that had proven feasibility and validity (HHSRF # EPC\_HKU-1A).

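### The safeguard against counting drugs and tests twice covers only GOPC and SOPC visits; if A&E and admission charges are also inclusive and their items are extracted, complication costs are overstated

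*Combined protocol and SAP*

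**What the plan says.** The section Direct Medical Costs of HT patients builds public cost from four items for each patient: dispensed drugs, laboratory tests and investigations, services (GOPC, SOPC, allied health and A&E), and admissions. The last part of that list reads "accident and emergency (A&E) department and 4) admissions to hospital in the 12 months before baseline". Unit costs come from the Gazette and the Hospital Authority ordinance "of charges for non-entitled persons". The only stated limit on the drug item is that "self-financed drugs will be considered as private medical cost"; no care setting is given for drugs or tests.

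Cost Analysis of RAMP-HT then gives the arithmetic. The general rule multiplies a unit price by a count of use: "The cost of each healthcare service will be derived by multiplication of the unit cost from Gazette and Hospital Authority ordinance". One exception is made to this rule: "the Government Gazette cost of each GOPC and SOPC attendance will be adjusted by a factor of 0.7 to include only the manpower cost". The purpose given for the exception is "To avoid double counting the cost of drugs and laboratory tests". The total is formed as follows: "The total public medical costs will be calculated by summing up all costs of drugs, laboratory tests and each healthcare service utilisation". No adjustment is stated for A&E or admissions.

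**The concern.** The plan itself recognises that a published attendance charge can already contain drugs and tests, and that itemising them as well counts them twice. Its remedy reaches two service types, but the sum covers every service. The text does not say whether the A&E and inpatient charges are free of drugs and tests, or whether the extract leaves out items issued in those settings. One of the two must hold for the total to be right there.

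Two primary outcomes depend on this total: direct medical costs by complication status, and the ICER. The average cost of each disease state enters the Markov model, and its assumption 6 gives both arms the same cost in the same state apart from the programme cost. The arms' other costs therefore differ only through the time spent in each state. If the gap between complicated and uncomplicated states is overstated, so is the saving credited to each avoided complication. The ICER is judged against one fixed threshold (HK$295,303 per QALY), and the text describes no sensitivity analysis of the unit costs that would reveal the error.

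**Working it through.** **The plan's own figure.** The factor 0.7 is taken from a cited annual report and cannot be derived from the documents. Its logic can be checked. For an outpatient charge C of which 0.3C is drugs and tests, all itemised:
- without the correction, C + 0.3C = 1.3C;
- with it, 0.7C + 0.3C = 1.0C.

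The correction does what is intended if the 30% removed is entirely drugs and tests. The plan says that what remains is manpower only, so the 30% may include other overheads. It is therefore not a clean estimate of the drug and test share even for outpatient visits.

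**Inputs for A&E and admissions.** None of these is in the documents; all are assumptions.
- b: share of the charge that is drugs and tests, range 0 to 0.4.
- c: share of those drugs and tests that is also itemised in the extract, range 0 to 1.
- h: share of a state's true public cost that is A&E plus inpatient care, range 0.3 to 0.9.

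**Step 1: the services themselves.** If the charge C is the true cost, the recorded cost is C + b × c × C, so recorded / true = 1 + b × c.

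| b | c = 0 | c = 0.5 | c = 1 |
|---|---|---|---|
| 0 | 1.00 | 1.00 | 1.00 |
| 0.1 | 1.00 | 1.05 | 1.10 |
| 0.2 | 1.00 | 1.10 | 1.20 |
| 0.3 | 1.00 | 1.15 | 1.30 |
| 0.4 | 1.00 | 1.20 | 1.40 |

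**Step 2: the cost of a complication state.** Overstatement = h × b × c. At c = 1 and b = 0.1 to 0.4:
- h = 0.3: 3% to 12%;
- h = 0.7: 7% to 28%;
- h = 0.9: 9% to 36%.

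**Step 3: the gap between states.** Suppose that an uncomplicated state truly costs 1 unit, 20% of it A&E plus inpatient, and a complicated state 4 units, 70% of it A&E plus inpatient. The A&E plus inpatient parts are 0.2 and 2.8, a difference of 2.6, and the true gap is 4 − 1 = 3. The gap is overstated by 2.6 × b × c / 3. At c = 1 that is 9%, 17%, 26% and 35% for b = 0.1, 0.2, 0.3 and 0.4. Both states are inflated; the gap widens because the complicated state contains more of this care.

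**Step 4: the ICER.** Let ΔH be the true difference between arms (RAMP-HT minus usual care) in discounted lifetime A&E plus inpatient cost. With b and c the same in every state, the incremental cost moves by b × c × ΔH. If RAMP-HT lowers that cost, ΔH is negative, the incremental cost is understated and the ICER favours RAMP-HT. QALYs are unaffected. The size cannot be computed, because ΔH is not in the documents.

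**The case against.** The strongest reply is that naming only GOPC and SOPC may be deliberate. The planners cite a source for the outpatient factor, and may have known that these were the only charges overlapping with the extract. The list of drugs and tests names no setting, and the instruction to sum all costs may mean all costs collected, not that ward or A&E items were collected. The detailed data schema is in Appendix F, which is listed but not part of the text available here; it may settle that point, and its absence is not a fault in the plan.

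This stands as far as it goes. A reader might infer that A&E and inpatient drugs and tests are likely counted twice, or that these services are costed at up to 130% of their true value. The documents support neither. Double counting needs both b and c above zero, and neither is shown. The 130% carries the outpatient 30% over to another kind of care and assumes that every item is also itemised; it is one assumed case, neither an estimate nor a bound.

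The direction of the ICER bias is also conditional. The modelled effect on complications lasts five years, after which both arms share the same transition probabilities. Inflation of the uncomplicated state, where RAMP-HT patients would spend more time, is a partial offset. Both features are contained in ΔH above: they limit the size, and the sign still depends on whether RAMP-HT lowers A&E and inpatient cost.

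The reply does not supply the missing statement. On either reading the written rule has no safeguard for A&E and admissions, and the text gives no reason why none is needed.

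**Conclusion.** The point holds in conditional form. As written, the correction covers GOPC and SOPC attendances only, while A&E and admissions are taken at the full charge from the same source and drug and test costs are added. If those charges include drugs and tests and those items are in the extract, the services are recorded at 1 + b × c times their true cost: 1.10 to 1.40 for an assumed b of 0.1 to 0.4 at full itemisation, and exactly 1.00 if either share is zero. Overstated complication costs and an ICER biased towards RAMP-HT follow only if, in addition, complicated patients use more A&E and inpatient care and RAMP-HT prevents complications. The first is reasonable but not quantified in the documents; the second is the study's hypothesis. The change is worth making because two primary outcomes depend on the total and because it alters nothing where the charges turn out not to be inclusive.

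**What to change.** In Cost Analysis of RAMP-HT, state for each Gazette or ordinance unit charge whether it includes drugs and tests, and state which care settings the drug and test extract covers. Then add a rule along these lines: where the A&E or inpatient unit charge is inclusive, itemised drugs and tests issued during those episodes are left out of the total.

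If episodes cannot be identified in the extract, adjust the charge by a factor justified for that service and vary it in a sensitivity analysis of the state costs and the ICER. The outpatient 0.7 should not be carried over by default: if the extract omits inpatient items, it would understate complication costs.

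The cost is one filter on episode type in the extract, if that field is available, and a few sentences in the plan. Cost totals become lower by an amount that depends on b and c, and stay the same if either is zero.

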#### Exclusion criteria

1. Patients who had a diagnosis of any HT complications defined by relevant ICPC-2 and/or ICD-9-CM diagnosis codes (defined in the "Methods" section) on or before baseline\*
2. Patients diagnosed to have Diabetes Mellitus (DM) on or before 31 March 2017, defined by ICPC-2 codes of T89 or T90
3. Patients exclusively managed by Specialist Out-Patient Clinic (SOPC) on or before baseline\*

To reduce selection bias, the RAMP-HT and usual care subjects will be matched in baseline covariates using the propensity score matching method:

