#### **Cost Effectiveness Analysis of RAMP-HT by Markov Modeling**

To evaluate the long term cost-effectiveness of RAMP-HT, a Markov model will be developed based on the natural history of a patient population, with similar distribution of age and gender as the RAMP-HT cohort, to simulate disease development over a lifetime. The structure of the model will be established as shown in Figure 1. At the end of each year, each HT subject may die, develop one HT complication or stay alive without complications. For subjects who develop complications, they may die immediately from the complication, die from other cause of death or stay alive in the complication health state.

The transition probabilities of developing complications and death from year to year will be estimated from the observed complication rates from the 5-year cohort study for RAMP-HT and usual care HT patients as described above. HT complication related mortality rates will be estimated by a review of published and unpublished local and overseas literature. Hong Kong standard life table will be used as a benchmark of survival presenting HT related mortality and mortality from other causes in Hong Kong local population among different demographic groups (e.g. age and sex). The cumulated life-years of the RAMP-HT and usual care cohorts will be calculated. The average cost and preference values for each HT disease state (with or without specific complication) obtained from the cost and

preference studies described above will be applied to the model to determine the cumulative quality adjusted life years (QALY) and lifetime costs for RAMP-HT and usual care cohorts.

The measure of cost-effectiveness of RAMP-HT will be the incremental cost-effectiveness ratio (ICER) in term of cost per QALY gained by RAMP-HT group compared to usual care. By comparing the between-group-differences in average lifetime costs ( $\Delta C$ ) and quality adjusted life years (QALYs) gained ( $\Delta E$ ), the ICER will be calculated by dividing the incremental cost ( $\Delta C$ ) by the incremental effectiveness ( $\Delta E$ ) in terms of QALYs gained by the RAMP-HT intervention compared to usual care. The ICER will be compared against the threshold value of 1 GDP (Gross Domestic Product) per capita of Hong Kong / QALY (HK\$295,303, 20137) to determine lifetime cost effectiveness of RAMP-HT.

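### Public costs are averaged per patient over fixed 12-month windows by complication status, with no person-time denominator or rule for the event and death years, and then used as yearly Markov state costs

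*Combined protocol and SAP*

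**What the plan says.** Section d(iv), Direct Medical Costs of HT patients, builds public costs from unit costs and the use of drugs, tests, services and "admissions to hospital in the 12 months before baseline and at 12, 24, 36, 48 and 60 months after study enrolment for each patient".

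Section d(v), Cost Analysis of RAMP-HT, summarises annual costs "at baseline and over each of 5 subsequent years, overall, and by the presence of complications". It adds that "The average annual public and private direct medical costs per patient will be analysed by HT complication status", and by study group.

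The Markov section then takes these averages as inputs: "The average cost and preference values for each HT disease state (with or without specific complication) obtained from the cost" and preference studies are applied to the model. Table 1 lists one direct medical cost per health status. The model moves subjects once a year. A subject who develops a complication may die of it at once, "die from other cause of death or stay alive in the complication health state".

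Exclusion criterion 1 removes "Patients who had a diagnosis of any HT complications defined by relevant ICPC-2 and/or ICD-9-CM diagnosis codes" on or before baseline. Under the CMS data extraction section, each patient is followed from baseline to the first outcome event or 31 March 2017.

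The text does not say when in a window complication status is set, whether the event year is split, whether the denominator is patients or person-time, or how the year of death is counted.

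**The concern.** The model charges a state cost for each year lived in the state. It therefore needs cost per person-year in the state. The plan describes a cost per patient per 12-month window, grouped by status. The two agree only if status never changes inside a window and nobody dies inside one. Here every complication begins during follow-up, so a window in which one starts normally holds both complication-free time and time with the complication. A window in which a patient dies holds less than a year of cost.

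Costs with and without complications and the ICER are both primary outcomes, and Hypothesis 3 compares costs by complication status. The cost difference between the states sets the saving credited to each complication that RAMP-HT avoids, so misplaced cost goes straight into the ICER. Censoring at the end of the study adds nothing to the problem: baseline is no later than 31 March 2012 and data run to 31 March 2017, so 60 months are observable unless the patient dies or leaves the system.

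**Working it through.** The plan states no state cost or person-time figure, so there is nothing to reproduce. The documents supply the windows, the exclusion of prior complications and the yearly cycle. The following are assumptions: first complications spread evenly over 5 years, a complication-free cost of 1 per year, an ongoing cost after the complication of 2 or 3 per year, and a one-off event cost as stated in each step.

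**1. Time in state, no deaths.** Take five patients, one with onset in the middle of each year.
- Windows with a complication present by the end: 5+4+3+2+1 = 15
- Person-years in state: 4.5+3.5+2.5+1.5+0.5 = 12.5
- Complication-free time inside those windows: 15 − 12.5 = 2.5 years

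**2. Status at window end, no event cost.**
- Ongoing cost 2: (12.5×2 + 2.5×1)/15 = 27.5/15 = 1.83, against 2.00 per person-year (8% low)
- Ongoing cost 3: (12.5×3 + 2.5×1)/15 = 40/15 = 2.67, against 3.00 (11% low)

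**3. Status at window start.** The complication state now has 4+3+2+1+0 = 10 windows, all wholly in state, so with no deaths and no event cost the averages are 2.00 and 3.00, without bias. With an event cost of 3 and ongoing cost of 2:
- Cost per person-year in state: (12.5×2 + 5×3)/12.5 = 40/12.5 = 3.20
- Window-start average: 2.00, a ratio of 0.63, with every event cost now in the no-complication state

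To see the other side, take 100 patients and the protocol's assumed 8% 5-year CVD incidence under usual care, ignoring ESRD and deaths. The 92 event-free patients give 92×5 = 460 windows. The 8 others average 15/5 = 3 windows each that start complication-free, which gives 24. Those 484 windows hold 480 complication-free years, 4 years in state and 8 events: (480×1 + 4×2 + 8×3)/484 = 512/484 = 1.06 instead of 1.00.

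**4. Event cost and direction.** The comparison changes when the benchmark is the ongoing cost that applies in later cycles.

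| Ongoing cost | Event cost | Window-end average | Per person-year in state | Window-end average vs ongoing cost |
|---|---|---|---|---|
| 2 | 3 | (27.5+15)/15 = 2.83 | 3.20 | 42% above |
| 3 | 4 | (40+20)/15 = 4.00 | (37.5+20)/12.5 = 4.60 | 33% above |

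The window-end average is below the person-year cost in both rows but above the ongoing cost in both.

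**5. Deaths.** A simulation of 400,000 patients used ongoing cost 2 or 3, event cost 0, 3 or 6, annual death hazard in state 0, 0.05 or 0.15, and terminal cost 0 or 3. Window average divided by cost per person-year in state:
- Status at window end, only windows entered alive: 0.79 to 0.92
- Status at window end, windows after death also counted: 0.69 to 0.92
- Status at window start, patients alive then, no event cost: 0.93 to 1.00

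Against the ongoing cost, the window-end average (windows entered alive) runs from 0.82 to 2.17 times, so the sign is open.

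**The case against.** The strongest reply is that the plan is silent rather than wrong. Setting status at window start, keeping only living patients, or splitting at the event date would all fit the text. A window-start rule also matches a model whose transitions happen at year end. The data schema in Appendix F, which is not in the text available here, might settle the matter.

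Much of this stands. A window-start rule gives a nearly unbiased ongoing cost. It does not remove the problem, because event costs then sit in the no-complication average. Markov assumption 6 applies the same cost per health status to both groups, apart from the RAMP-HT cost, so avoiding an event would earn no credit for the event cost itself. Only splitting the event year, which the text does not mention, avoids misplacement under either rule.

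A second reply is that a pooled cost per person-year would not be better by itself. In the last row of the table it gives 4.60 where the ongoing cost is 3, further away than the 4.00 from windows. That is correct, and it is why event-year and later-year costs must be separated as well.

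Two narrower replies also stand. Private costs come from telephone respondents, so time after death cannot enter them. And if complication costs are understated, the test of Hypothesis 3 becomes conservative, not falsely positive.

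**Conclusion.** The point holds as a mismatch between the cost the plan describes and the cost its model needs, with no stated rule to bridge the two. With even onset, no deaths and no event cost, status at window end lowers the complication-state cost by 8% at an assumed cost ratio of 2 and by 11% at 3. Status at window start moves event costs to the no-complication state. All sizes rest on assumed costs, onset and mortality.

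Three stronger readings are tempting, and the documents do not support them:
- **Time after death is counted.** The text does not say so; this would be inferred from silence.
- **Status means ever having a complication in 5 years.** A reader might infer this from the baseline summary by presence of complications, since nobody has one at baseline. It would give 37.5/25 = 1.50 against 2.00 (25% low) or 50/25 = 2.00 against 3.00 (33% low), and more with deaths. But the complication split can be read as applying to the follow-up years only.
- **The ICER is biased against RAMP-HT.** This would follow if complication costs were simply understated. Pooling event costs into one lifetime state cost can overstate later cycles, so the net direction is not established.

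**What to change.** In Cost Analysis of RAMP-HT, state that each patient's public-cost record is split at the date of first complication and at death. Allocate each dated service, drug and admission to the state occupied on that date, and divide the total in each state by person-years in that state. Estimate event-year and later-year costs separately, counting the event year from onset, and enter both in the Markov model in place of the single cost per complication state in Table 1.

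State also that the baseline cost summary is not split by complication status, or that it is split by future status and not used in the model.

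The cost is some programming, a small change to the model inputs, and a need for dated service records in the CMS extraction. First-event times are already needed for the Cox and Kaplan-Meier analyses, and deaths come from the Death Registry. That service records carry dates is an assumption until checked against Appendix F; the timeline's step for confirming the data schema (months 0-4) is the natural place to check. No new patients or procedures are required.
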